## Study Summary

Title	A Prospective, Open-Label, Parallel Study Evaluating the Effect of an Adjunctive Anti-Seizure Medication using a Glutamatergic Modulator in Patients with Focal Epilepsy and High-Grade Glioma
Running Title	Adjunctive Anti-Seizure Drug (ASD) in Drug-Resistant Focal Epilepsy and high-grade glioma
Protocol Number	19-006286
Phase	IV (investigator-initiated)
Methodology	This is an open-label, parallel study evaluating the effect of PER in patients with biopsy-proven high-grade glioma (grade II and above) and focal epilepsy. Dose ranging will be based on best clinical practice in patients with drug-resistant focal epilepsy.
Overall Study Duration	18 months
Subject Participation Duration	Subject will participate in study procedures for a total duration of 12 months including a 2-to-4-week titration phase, 12-week minimum and 24-week maximum stable treatment phase for interim analysis, and 40 weeks of total treatment time at study termination.
Single or Multi-Site	Single Site
Primary Objectives	To evaluate the efficacy and safety of PER on seizure frequency in adult patients with biopsy-proven high-grade glioma and focal epilepsy compared with alternate ASDs.
Secondary objectives	To assess the progression of biopsy-proven high-grade glioma in patients prescribed a daily dose of 4-8mg of PER for 40 weeks in patients with focal epilepsy when compared with alternate ASD  To assess the change in neurocognitive function and brain MRI progression over the course of PER treatment with a daily dose of 4 mg (up to - 8mg) in patients with biopsy-proven high-grade glioma and focal epilepsy compared with alternate ASDs.  To identify a biomarker-specific response to seizure-reduction in patients treated with PER in patients with a biopsy-proven high-grade glioma (i.e., IDH-mutant vs wildtype).

Number of Subjects	20
--------------------	----

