Study Product, Dose, Route, Regimen	PER is a noncompetitive AMPA glutamate receptor antagonist. The two phases of the treatment portion of this study include a titration phase and a stable dosing phase. This study will have two treatment arms consisting of PER and alternative ASD arm. The PER arm will begin a titration phase with 2mg PER PO q.d. (may be split to b.i.d.) for one week and increase by 2mg/week until reaching an initial dose of 4mg PO q.d. (q.d. or b.i.d. dosing) is reached. Flexible dosing of PER above 4mg to a maximum of 8 mg daily will be compared to use of alternative ASDs and be guided by best clinical practices with dosing and indication within U.S. FDA guidelines.
Duration of Administration	Participants will be assigned to receive open label PER or an alternate ASD for at least 12 week and up to 40weeks for the remainder of the study. This includes 2-4 weeks of titration and up to 40 weeks of stable dosing. Reduction by 2 mg will be allowed in cases of efficacy if doses greater than 4 mg daily result in non-idiopathic side-effects.
Reference therapy	All comparisons will use standard ASDs as the reference therapy using an intent to treat study design for patients initiating or tapering off PER therapy.
Statistical Methodology	Statistical analysis will include Student T-test, Chi-square for categorical differences. An interim analysis will be performed when half of the targeted subjects are enrolled.

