Because of shared pathways, current anti-seizure drugs (ASDs) may affect treatment of patients with brain tumor, and various antitumor therapies are valuable for seizure management. Mechanisms involving cysteine-glutamine transporters, for example, regulate glutamate release and return through cellular exchange. One explanation for the close link between seizures and glioma evolution are elevated extracellular glutamate levels in the peri-glial and -neuronal space with ensuing over-activity of  $\alpha$ -amino-3-hydroxy-5-methyl-4-isoxazolepropionic acid (AMPA) and N-methyl-d-aspartate (NMDA) receptors in both conditions. Recent studies point to the role of glutamate in excitotoxic damage resulting in seizures as well as maintenance and invasion of malignant glioma. Blockade of this system could lead to pharmaceutical development that could affect the excitotoxicity of both high-grade glioma and brain-tumor related epilepsy. Human trials of PER demonstrate safety and efficacy as an adjunctive therapy for adult patients with epilepsy. Limited information is available to demonstrate effectiveness in subpopulations associated with excessive glutamatergic stimulation such as brain tumor. PER, a FDA approved AMPA antagonist cleared for clinical use, may have immediate impact in 80,000 patients with brain tumors, and 3.4 million Americans with epilepsy (commonly co-morbid conditions). Anecdotal benefit has been reported in epilepsy patients with primary brain tumor and low dose PER (Vecht et al., 2017). Cognitive decline frequently complicates treatment of patients with high-grade glioma and also in patients with epilepsy impairing overall QoL.

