### 5.3 Method for Assigning Subjects to Treatment Groups

Participants will be assigned to receive:

Group A: open label arm of adjunctive PER (study drug) for patients with seizures treated with at least 1 ASD administered in escalating divided doses of 2 mg/week to 4 mg daily with flexible dosing to 8 mg/day by 4 weeks. Subjects must undergo forced titration of 2 mg/week and be able to tolerate 4 mg to continue in the study. Concomitant ASD will be utilized according to best clinical practice.

or

Group B: continued open label treatment for patients with seizures treated with at least 1 ASD, as per best medical practice, without the use of PER.

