#### Handling of Missing Data

Study data will be collected and managed using REDCap electronic data capture tools hosted at Mayo Clinic. All data requested on the Case Report Form (CRF) will be recorded for each participant. A standardized CRF will be generated by REDCap. For any data query, the Principal Investigator and Investigators will meet to clarify the data queried and make corrections based on consensus. Once the study is completed, the Principal Investigator will randomly select 3 participants and compare the data documented for each on the CRF with what is entered into the REDCap database. If there is any discrepancy, the Principal Investigator and/or Investigators will cross-reference all 20 patients to ensure accuracy.

**Primary Hypothesis:** We hypothesize that perampanel will lead to a significant reduction in seizure frequency for adult patients with brain tumor-related seizures associated with high-grade glioma.

We will compare seizure frequency before and 3 months after treatment with monotherapy and adjunctive PER and use descriptive statistics to demonstrate differences in responders. A P-value < 0.05 will be used to reflect statistical significance.

**Secondary Hypothesis 1:** We hypothesize the progression of brain tumor (comparing 4 and 8 mg/d of perampanel) based upon fusion by comparing baseline brain MRI and MRI at 12 months will be less for IDH-mutants.

We hypothesize there will be minimal or no change in neurocognitive function from 0 to 3 months on Montreal Outcome Cognitive Assessment (MOCA; higher scores indicating greater function); and the Clinical Global Impression of Change (CGIC; scores from 1 to 7, with lower scores indicating greater improvement and a score of 4 indicating no change).

Chi-square and Student T-test will be used to measure differences in assessment and change during the study period. A P-value < 0.05 will be considered significant.

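### Secondary Hypothesis 1 includes a 4 versus 8 mg/d comparison of tumor progression, but no dose groups exist and attained dose is a clinical choice, so the contrast is confounded as written

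*Combined protocol and SAP*

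**What the plan says.** Secondary Hypothesis 1 stands in section 7.2, under the Handling of Missing Data heading. It begins "We hypothesize the progression of brain tumor (comparing 4 and 8 mg/d of perampanel" and ends by predicting that progression, judged by "comparing baseline brain MRI and MRI at 12 months will be less for IDH-mutants". One sentence thus carries a dose comparison and an IDH prediction. The same subsection later assigns chi-square and Student t-tests to differences in assessment and change, with P < 0.05 considered significant. It mentions no covariate adjustment.

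Dose is described elsewhere as follows:

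- Study Summary, Methodology: "Dose ranging will be based on best clinical practice in patients with drug-resistant focal epilepsy".
- Study Summary, Study Product: "Flexible dosing of PER above 4mg to a maximum of 8 mg daily will be compared to use of alternative ASDs". The comparator named here is other drugs, not another perampanel dose.
- Study Summary, Duration of Administration: "Reduction by 2 mg will be allowed in cases of efficacy if doses greater than 4 mg daily result in non-idiopathic side-effects".
- Section 5.3: Group A is a single arm taken from "2 mg/week to 4 mg daily with flexible dosing to 8 mg/day by 4 weeks".

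Section 4.3 puts 10 patients in the perampanel group and leaves the choice of group to the treating physician. The objectives in the Study Summary and section 2 compare MRI progression on perampanel with progression on alternate ASDs. None compares doses.

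**The concern.** A comparison of two doses can be read as a dose effect only if something unrelated to prognosis decided who got which dose. Here the treating clinician decides, after treatment has started. A clinician may raise the dose in patients doing badly, or may be able to raise it only in patients well enough to tolerate it. Either habit ties dose to severity. The protocol's own background, section 1.1, ties seizures to the tumor: "One explanation for the close link between seizures and glioma evolution are elevated extracellular glutamate levels". If dose follows severity and severity predicts MRI progression, the 4 and 8 mg/d groups will differ even when dose does nothing.

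The groups are also undefined. The plan does not say whether starting, modal, maximum or final dose places a patient, nor where a patient on 6 mg or with a changing dose belongs.

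At stake is a P-value on tumor growth by dose, from a pilot that section 7.1 says is meant to establish feasibility for a larger multi-center trial.

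**Working it through.** **1. The plan's own figure.** There is no power calculation to reproduce. Section 7.1 gives 20 patients as a feasibility target, and section 4.3 splits them 10 + 10 = 20. The ceiling for any dose contrast is the 10 patients in Group A.

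**2. Inputs.**

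- From the documents: 10 perampanel patients; t-test or chi-square without adjustment; P < 0.05.
- Assumed, because the documents give no value: a two-sided test; a 5/5 split between 4 and 8 mg/d with nobody in between; progression with SD 1; a latent severity with correlation r1 to the dose chosen and r2 to MRI progression.

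**3. Formula under no dose effect.** If the upper half on a dose-choice score goes to 8 mg, the large-sample spurious difference is

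difference = 2 × 0.798 × r1 × r2 = 1.596 × r1 × r2 (in SD of progression).

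- r1 = r2 = 0.3: 1.596 × 0.09 = 0.14
- r1 = r2 = 0.5: 1.596 × 0.25 = 0.40
- r1 = r2 = 0.7: 1.596 × 0.49 = 0.78
- r1 = 1, r2 = 0.3: 0.48
- r1 = 1, r2 = 0.5: 0.80

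The last two rows are the extreme in which severity alone decides dose.

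**4. The same at 5/5.** Simulating the planned t-test in 10 patients (100,000 runs or more per case) gives slightly smaller differences, because a split of 10 separates the halves less:

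| r1 / r2 | Mean spurious difference (SD) | False positives |
|---|---|---|
| 0 / 0 | 0.00 | 5.1% |
| 0.3 / 0.3 | 0.13 | 5.4% |
| 0.5 / 0.5 | 0.37 | 8.2% |
| 0.7 / 0.7 | 0.72 | 18.9% |
| 1 / 0.3 | 0.44 | about 10% |
| 1 / 0.5 | 0.74 | about 20% |
| -0.7 / 0.7 | -0.72 | 19.0% |

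Positive values make 8 mg/d look worse. The last row is the case where sicker patients stay on the lower dose, and there 8 mg/d looks better. A 7/3 split gives the same pattern (16.9% false positives at 0.7/0.7).

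**5. Masking.** Suppose 8 mg/d truly reduced progression by 0.8 SD. The mean observed difference is -0.80 SD at 0/0, -0.43 SD at 0.5/0.5 and about -0.08 SD at 0.7/0.7. Significant results in the right direction fall from 20% to about 9% and 3.3%.

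**6. Precision without any bias.** With dose unrelated to severity, a 5/5 t-test needs a true difference of about 2.0 SD for 80% power, and a 7/3 split about 2.2 SD.

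**7. Sample size is not the cure.** With 50 per group and no dose effect, false positives are 10.8% at 0.3/0.3, 51.8% at 0.5/0.5 and 98.7% at 0.7/0.7. Repeating this contrast in a larger trial would make the bias more likely to reach significance.

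**The case against.** Several points on the other side have weight.

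*The parenthesis may be loose wording for the 4 to 8 mg range.* The sentence predicts less progression in IDH-mutants, and the objectives describe a daily dose range. This could be right. But the sentence says that the two doses are compared, and if no comparison is meant, removing the phrase loses nothing.

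*No passage names a dose test.* This stands in part. The test and P-value lines follow the paragraph on MOCA and CGIC. They plausibly extend to MRI change, which is a change during the study period, but the plan does not say so.

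*A reader might infer that seizure course drives the dose.* The documents do not support that as fact. They give no rule for raising the dose, and the only named trigger is side effects, for lowering it. Section 5.3 has flexible dosing to 8 mg/day by week 4, and section 4.1 admits patients with as few as 1 seizure in 3 months, so few seizures may be available to guide dose. Much of the confounding may come from baseline severity. That is still confounding.

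*A reader might infer a breach of intent-to-treat.* Section 3.4 and the Study Summary apply that rule to patients initiating, exiting or tapering off perampanel. Neither addresses dose within the arm, and section 7.3 separately names a protocol-compliant population. The point does not rest on this.

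*The large bias figures are extreme.* This stands. Differences of 0.48 and 0.80 SD need severity alone to sort patients by dose, and at 0.3/0.3 the distortion is small.

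**Conclusion.** The point holds in limited form. As worded, the hypothesis contains a comparison of 4 and 8 mg/d for which the design provides no groups, no assignment, no stratification and no adjustment. A difference could appear with no dose effect, and a real effect could be masked.

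The direction cannot be known from the documents, and the size is conditional on correlations they do not give. It is close to negligible at 0.3/0.3, moderate at 0.5/0.5, and large only when dose follows severity closely or the correlations approach 0.7. The figures also assume a clean 5/5 split; patients at 6 mg would shrink the groups further.

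Severity is minor to moderate. This is one phrase in a secondary hypothesis, in a pilot that section 7.1 says is not powered for effectiveness. Low power does not excuse the contrast, because low power is imprecision and this is bias. Nothing here implies a view on which dose is right.

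**What to change.** Delete the parenthesis on 4 and 8 mg/d from Secondary Hypothesis 1. Analyse MRI progression with all Group A patients together, whatever dose they reach, and name two contrasts: perampanel versus alternate ASD, which the objectives call for, and IDH-mutant versus wildtype, which the hypothesis itself predicts. The first contrast is also not randomised (section 4.3) and should be reported with that caution. The MRI date in the same sentence needs reconciling with the Schedule of Events, whose last MRI is at Day 300.

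If dose is shown at all, give a listing per patient of dose history, reasons for each change, and baseline tumor and seizure status, without a P-value or a dose-effect claim. Setting early dose against later MRI change would not be a substitute. It repairs the time order but not the confounding, drops patients without a Day 90 MRI, and changes the outcome window.

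The cost is a wording change and, if wanted, one listing. The loss is a dose comparison that this design cannot support.

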### 1.1 Background

Does the novelty of Perampanel's unique mechanism of action demonstrate anti-seizure efficacy, tumor-cytotoxic activity, and impact progressive impairment in neurocognitive function in patients with high-grade glioma? The major reasons why this study should be conducted include:

1. Seizures commonly occur in 40% to 70% of patients with a primary brain tumor/glioma.
2. PER is FDA approved for adults with focal seizures.

3. PER has novel and unique mechanisms of action that include a primary effect on excitatory amino acids/AMPA.
4. Glutamate-induced excitotoxicity and disruption of intracellular communication hold a key role in the progression of disease in patients with glioblastoma (altered cysteine-glutamate transport).
5. Glutamate induced over-activity is also suspected to influence high-grade glioma growth.
6. Studies show that isocitrate dehydrogenase 1 (IDH1) mutant gliomas are more likely to cause seizures than IDH1 wild-type gliomas. The IDH1 mutation has been associated with tumorigenesis and has implications relative to differential treatment for primary brain cancer and prognosis.

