### Secondary Objective

To assess the change in neurocognitive function and brain MRI progression over the course of PER treatment with a daily dose of 4 mg (up to -8mg) in patients with biopsy-proven high-grade glioma and focal epilepsy compared with alternate ASDs.

To identify a biomarker-specific response to seizure-reduction in patients treated with PER in patients with a biopsy-proven high-grade glioma (i.e., IDH-mutant vs wildtype).

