### **3.5 Identification of Source Data**

Electronic medical records will be maintained via a RedCAP database for consecutive and prospective collection of data.

Efficacy measures used in the study include: clinical assessments will include serial brain MRI, EEG, anti-seizure drug levels and subject self-assessment at clinical follow-up; Neurological Disorders Depression Inventory for Epilepsy (NDDI-E), assessment for screening of depression PHQ-9;Montreal Outcome Cognitive Assessment (MOCA); Clinical Global Impression of Change (CGIC) score; Columbia –Suicide Severity Rating Scale. Seizure calendars performed at 2 months prior to initiation of therapy or adequate reliable historical baseline, and then monthly during study; and QOLIE-31, (see schedule of events for frequency of assessment).

Anatomic brain MRI with perfusion scanning/gadolinium will be obtained at 3 months and then every 3 months, to examine the correlated progression of brain tumor, or the absence of tumor. Laboratory studies will be employed before and after PER initiation. EEG will be obtained at baseline and at 3 months and 12 months to identify changes in background activity (e.g. diffuse slowing) and epileptiform discharges to correlate with focal seizure presence vs absence. Neuropsychological batteries will determine the presence or absence of significant anxiety, depression or cognitive changes over time and quality of life inventory will be obtained at the beginning, intermediate and end of the trial.

The following source data will be directly recorded on the Case Report Form (CRF):

- A comprehensive History and Physical examination and Neurological examination will occur at the initial screening/baseline.
- Clinical visitation will occur at screening/baseline, 3, 6, and 12 months.

Survey questionnaires will be obtained at baseline, 3, 6, 9, and 12 months. The following source data will not be directly collected in the Case Report Form (CRF), but will be captured in supportive documentation (study source documents, EMR):

- Laboratory studies will be employed at baseline and at each clinical visit after PER initiation.
- Brain tumor tissue will be assessed for the usual molecular markers (i.e., IDH-mutant vs wildtype, MGMT methylation, ARX).
- 12-lead ECG will be obtained at baseline and as clinically indicated
- Anatomic brain MRI with and without gadolinium will be obtained at baseline and follow-up brain MRI at 3 months and 6 months during PER use.

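### The IDH objective concerns seizure reduction under PER, but section 7.2 specifies no IDH-by-seizure analysis and instead tests tumour progression by IDH status and flexible PER dose

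*Combined protocol and SAP*

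**What the plan says.** **Objective.** The Study Summary and section 2 both list this secondary aim: "To identify a biomarker-specific response to seizure-reduction in patients treated with PER in patients with a biopsy-proven high-grade glioma (i.e., IDH-mutant vs wildtype". The outcome is seizure reduction and the population is patients on PER.

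**Analysis.** In section 7.2, IDH appears once, in Secondary Hypothesis 1 (printed under Handling of Missing Data): "We hypothesize the progression of brain tumor (comparing 4 and 8 mg/d of perampanel) based upon fusion by comparing baseline brain MRI". The sentence then names the second scan and the direction it predicts: "and MRI at 12 months will be less for IDH-mutants". Chi-square and t-tests at P<0.05 follow for the secondary hypotheses. The primary seizure analysis in the same section will "use descriptive statistics to demonstrate differences in responders" and does not mention IDH. Neither do the endpoints in section 3.4. There is no Secondary Hypothesis 2.

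**Progression objectives.** The Study Summary lists glioma progression on 4-8 mg PER. The Study Summary and section 2 both list brain MRI progression. All of these are comparisons with alternate ASDs.

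**Dose.** In Group A, PER is "administered in escalating divided doses of 2 mg/week to 4 mg daily with flexible dosing to 8 mg/day by 4 weeks" (section 5.3). The Study Summary says dosing follows best clinical practice and allows a 2 mg reduction for side effects above 4 mg. Group B receives no PER.

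**Marker.** Section 1.1 says the IDH1 mutation "has implications relative to differential treatment for primary brain cancer and prognosis" and that mutant gliomas are more likely to cause seizures. Section 3.5 states: "Brain tumor tissue will be assessed for the usual molecular markers (i.e., IDH-mutant vs wildtype, MGMT methylation, ARX"; it does not say in which group.

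**The concern.** A statistician who followed section 7.2 would have no instruction for the IDH seizure objective. The IDH analysis that is written down has a different outcome and a different contrast, and it carries a significance threshold.

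That contrast is also hard to interpret, for two reasons:

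- It is confined to PER patients, while the protocol itself calls IDH status prognostic. A finding of less progression in IDH-mutants could therefore reach a report, or the planning of the multi-center trial that this pilot is meant to inform, as a PER-related biomarker signal.
- It groups patients by a dose reached after baseline, so a difference between 4 and 8 mg/d reflects in part who could be moved up or had to be moved down.

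**Working it through.** **Step 1. Set the objective and the analysis side by side.**

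| | Objective (Study Summary, section 2) | IDH hypothesis (section 7.2) |
|---|---|---|
| Outcome | Seizure reduction | MRI tumour progression |
| Contrast | IDH-mutant vs wildtype | IDH-mutant vs wildtype, and 4 vs 8 mg/d |
| Patients | Treated with PER | On 4 or 8 mg/d PER |
| Time | Not stated; section 3.4 uses 3 and 6 months for responders | Baseline to 12 months |

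The outcome differs, and 4 versus 8 mg/d appears in no objective. The last visit in the Schedule of Events is Day 300, and 300 / 30.44 = 9.9 months, so no 12-month MRI is scheduled.

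**Step 2. Sample size.** The stated total reproduces only as a sum: 10 + 10 = 20 (section 4.3). Section 7.1 gives no effect size or power and calls the study a pilot.

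**Step 3. Dose cells.** Steps of 2 mg from 4 to 8 mg pass through 6 mg, which fits neither dose group. IDH (2) by dose (4/6/8) gives 6 cells for 10 PER patients. With 4 and 8 mg only, 10 / 4 = 2.5 patients per cell on average.

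**Step 4. Prognosis alone can satisfy the hypothesis.** Assumed progression rates: 0.3 in mutants and 0.7 in wildtype, in both groups, with no PER effect.

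- Within PER: 0.3 - 0.7 = -0.40, the direction predicted.
- Difference of differences: (0.3 - 0.7) - (0.3 - 0.7) = 0.

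**Step 5. What an IDH-by-responder table can show.** The documents give no IDH prevalence or responder rates, so these are assumptions.

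- *5/5 split, 4/5 vs 1/5 responders.* With five responders in ten there are C(10,5) = 252 arrangements. Those at least as extreme number 2 x (C(5,4) x C(5,1) + C(5,5) x C(5,0)) = 2 x (25 + 1) = 52. Two-sided Fisher p = 52/252 = 0.206.
- *Exact 95% interval for 4/5.* The lower limit solves 5p^4(1-p) + p^5 = 0.025, so p = 0.28. The upper limit is 0.975^(1/5) = 0.995. By symmetry, 1/5 gives 0.005 to 0.72.
- *Exact Fisher power, two-sided 0.05, within the 10 PER patients:*

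| Mutants | 0.7 vs 0.3 | 0.8 vs 0.2 |
|---|---|---|
| 1 | 0.00 | 0.00 |
| 2 | 0.03 | 0.11 |
| 3 | 0.11 | 0.30 |
| 4 | 0.15 | 0.38 |
| 5 | 0.15 | 0.38 |

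With one mutant the smallest attainable p is 0.10.

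**Step 6. Would Group B settle it?** At p = 0.5 with m mutants of 10 in each group, the SE of the difference of differences is sqrt(2 x 0.25 x (1/m + 1/(10-m))).

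- m = 5: SE 0.447, 95% half-width 1.96 x 0.447 = 0.88.
- m = 2: SE 0.559, half-width 1.10.

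Now suppose a rule that calls the response PER-specific whenever the IDH difference in PER exceeds that in Group B. If responder rates are 60% (mutant) and 30% (wildtype) in both groups, the two differences are independent draws from one distribution, so P(exceeds) = (1 - P(tie)) / 2. Enumeration gives:

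- 5/5 split: P(tie) = 0.186, so P(exceeds) = 0.41.
- 3/7 split: P(tie) = 0.074, so P(exceeds) = 0.46.

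**The case against.** **It is a small pilot.** Section 7.1 says the study is not powered for effectiveness. That excuses the low power in step 5. It does not explain why a stated objective has no analysis while a different question is tested at P<0.05.

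**The objective can still be answered.** A reader might infer that the trial will yield nothing on IDH and seizures. That is too strong. Seizure diaries and tumour markers are collected, and chi-square is planned for categorical differences, so a table could be made. What stands is that nobody has specified it.

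**The hypothesis claims only less progression in mutants.** This is fair. It does not assert a PER-specific effect, and if mutants progress less it is correctly met as worded. The problem lies in what may be read into the result.

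**IDH and seizure response.** A reader might infer that an IDH difference in responders under PER is to be expected even if PER does nothing specific. The documents do not support that. Section 1.1 speaks of seizure occurrence and prognosis. The endpoint is reduction from the patient's own baseline, in patients who all have refractory seizures at entry. The prognosis argument applies to progression.

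**Dose and seizure control.** A reader might also infer that dose follows seizure control. The documents say best clinical practice, with reduction for side effects. Dependence on tolerability is stated; dependence on seizure control is only plausible.

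**Conclusion.** The point holds. Section 7.2 specifies no analysis for the IDH seizure objective, and its one IDH hypothesis tests a contrast that matches no objective, excludes Group B, and groups patients by a non-assigned dose with 6 mg unclassified. Less progression in IDH-mutants within PER cannot be attributed to PER. The mismatch and the dose problem rest on the text alone; the size of any misleading difference (0.40 in step 4) rests on assumed rates.

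It is tempting to conclude that comparing the IDH difference in PER with that in Group B would isolate a PER response. It would not. The treating physician chooses who receives PER (section 4.3), the half-width is about 0.88 to 1.10, and a bare exceeds-Group-B rule would be met by chance about 41% to 46% of the time under the assumed 60%/30% rates in both groups.

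This should be corrected, but it concerns a secondary aim of a 20-patient pilot and does not affect the primary analysis.

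**What to change.** In section 7.2:

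1. Add a descriptive table of >50% seizure reduction at 3 and 6 months by IDH status within PER, with exact intervals and no P<0.05 claim. Show the same table for Group B as context where IDH status is available. The sponsor should confirm that markers are collected in both groups, because section 3.5 does not say so. If a log seizure rate is also used, give a rule for zero counts.
2. Show MRI progression by IDH status in both groups in the same way. Reconcile the 12-month MRI with the last scheduled visit at Day 300.
3. Drop 4 versus 8 mg/d as a hypothesis test. List the dose reached, including 6 mg, descriptively only.
4. State that, with physician-chosen assignment and about 10 patients per group, neither the PER-only IDH difference nor its difference from Group B identifies a PER-specific biomarker response. Adopt no exceeds-Group-B decision rule.

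The cost is plan wording and a few descriptive tables, with no added patients. Marker data need no extra work if both groups are already covered. The downside is that the IDH result becomes explicitly exploratory.
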